Lipid intake in the neonatal period is crucial for retinal and brain development along and an important source of calories for growth [16]. Due to this essential nature of lipid intake during the neonatal period, concern has been raised regarding lipid restriction and its effects on neonatal growth and neurodevelopmental outcomes. Studies investigating neurodevelopmental outcomes of infants treated with lipid restriction have shown development within normal ranges for the patient's age and similar to those of patients treated with standard soy-based lipid dosing [17, 18]. Studies have shown mixed results with regards to growth and neonates treated with lipid restriction. Rollins et al showed a greater increase in weight z-score for patients on standard soy-based dosing compared to reduced dosing, but found no difference in length or head circumference [13]. Other studies have found similar growth when comparing patients both in the neonatal period and into early childhood [18, 19]. The role of the various lipid strategies in the prevention of IFALD is still unclear at this time. Further studies are needed to better understand this disease, its prevention, and its outcomes. During this study we hope to compare two possible preventative strategies and determine a future direction for studying Smoflipid and soy-based lipid reduction.

Specific Aim

This study is designed to be a single center, pilot study to evaluate the prevention of cholestasis in neonates requiring abdominal surgery with intestinal failure, divided into two treatment groups, one receiving composite lipid emulsion (Smoflipid® 20%) at standard dosing and the other receiving soy-based lipid (Intralipid® 20%) at reduced dosing. The rate of cholestasis development in the two treatment groups will be compared to a historical control cohort which received soy-based lipid (Intralipid® 20%) at standard dosing of 2 to 3 g/kg/d .

Study Objectives

1. Primary: The primary objective of this study is to determine the number of infants receiving Smoflipid at typical dosing (2-3 g/kg/d) and the number of infants receiving Intralipid reduction (1 g/kg/day) that develop cholestasis compared to historical controls receiving Intralipid at standard dosing (2-3 g/kg/day). Cholestasis will be defined as direct bilirubin greater than 2 mg/dL for at least two measurements, 5-7 days apart.

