- AST or ALT greater than 5 times the upper limit of normal within 2 weeks of enrollment

- Direct bilirubin greater than 2 mg/dL on any consecutive measurement 5-7 days apart within 2 weeks of enrollment
- Severe coagulopathy with elevated INR greater than 2.0 or clinically significant bleeding as determined by the primary and research teams
- Culture confirmed sepsis with positive blood, urine, or CSF culture within 2 weeks (14 days) of enrollment
- Renal failure requiring dialysis
- Cyanotic heart disease requiring prostaglandin therapy
- Hypertriglyceridemia (greater than 250mg/dL) at time of enrollment

Enrollment/Randomization

A maximum total of 50 prospective patients, 25 per arm, will be enrolled in the study. Patients will be eligible for enrollment if they meet the above listed enrollment criteria. Once patients are determined to meet enrollment criteria, the parents of the patient will be approached and informed consent will be obtained. Please see separate informed consent document for full consent details.

Stratified randomization will be used to divide patients into each treatment group. Patients will be initially stratified based on the diagnosis of necrotizing enterocolitis or spontaneous intestinal perforation (ischemic/perforation group) or anatomic intestinal abnormality. Once stratified based on diagnosis, patients in each stratum will then be randomized to receive either Smoflipid or Intralipid reduction as described below. Group randomization will be based on premade concealed envelopes.

This study will not be blinded as the caloric dose of the lipid strategies will vary and potentially influence other TPN dosing. Both IV lipids will be given as a solution separate from the remaining TPN. This separate IV lipid will be given as two 12 hour infusions over a 24 hour period.

In the event of slower than anticipated patient enrollment, a minimum of 24 patients (12 per treatment group) will be enrolled in order to obtain needed feasibility data.

Historic Controls

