A group of 24 patients previously treated in the Riley NICU from the years 2016 – 2017 will be used as a historic control cohort. Historic patients will be eligible for enrollment in the study if they have one of the above listed diagnoses, received post-operative parenteral nutrition, and were treated with soy-based lipid at standard dosing (2-3 g/kg/day). Historic patients will be ineligible to participate if any of the above listed exclusion criteria are true at the time of their abdominal surgery. Historic patients will be matched to prospective patients when able. This matching will first utilize in order: 1. days of parenteral lipid therapy, 2. diagnosis, 3. birth gestational age, and 4. birth weight when selecting for inclusion.

Study Procedures

1. Smoflipid® (20% lipid emulsion) treatment group
 - a. Advancement:
 - i. Smoflipid will be started at 1 g/kg/d on day 1 of parenteral nutrition after enrollment and advanced by 1 g/kg/d each subsequent day to a goal maximum of 3 g/kg/d
 - b. Maintenance and weaning [8]:
 - i. The Table below will be used as a guide for weaning Smoflipid as enteral nutrition is initiated and advanced.
 - ii. Patients will continue to be monitored by a clinical dietitian and pharmacist as per standard of care. Pending their recommendations, along with the clinical state of the child, the actual dose of Smoflipid needed may vary by individual patient.
 - c. Other parenteral nutrition components
 - i. Amino acid will be provided to meet estimated protein requirements only and will not be increased as a form of caloric intake.
 1. Term infant approximate goal of 3 g/kg/day and preterm infant approximate goal of 3.5 – 4 g/kg/day.
 - ii. Glucose infusion will be utilized and advanced per standard protocol to provide remainder of estimated non-protein caloric need of each individual patient.
 1. Maximum glucose infusion rate (GIR) while enrolled in study of 16 mg/kg/min. If further caloric intake is required, Smoflipid will be increased to a maximum of 3 g/kg/d.

Table 1: Smoflipid dosage recommendations for weaning as enteral feeds advanced

% calories from PN	Volume enteral feeds (ml/kg/d)	Enteral calories (kcal/kg/d)	Lipid (g/kg/d)
80-100%	\leq 20-40	\leq 30	3
60-80%	40-60	30-40	3
50-60%	60-80	40-50	2.5
40-50%	80-100	50-60	2
30-40%	100-110	60-70	1.5
20-30%	120	70-90	1
<20%	>120	>90	0

2. Intralipid® (20% lipid emulsion) reduction treatment group
 - a. Advancement:
 - i. Intralipid:

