 - i. Each patient's chart will be reviewed for documentation of retinopathy of prematurity or bronchopulmonary dysplasia (chronic lung disease). The absence or presence of these diseases at the time of discharge will be noted for each study patient, particularly those patients born prematurely at less than 37 weeks gestation.
- d. Length of Stay:
 - i. An ICU length of stay will be calculated for each patient based on their admit date and discharge date from the Riley NICU.
 - ii. For patients transferred to another unit prior to discharge the transfer date will also be documented. For these patients a NICU length of stay and total hospital length of stay will be calculated.
- e. Laboratory monitoring (see Table 2 below for reference schedule):
 - i. Effort will be made to draw all study lab tests along with other standard of care, routinely scheduled labs.
 - ii. The schedule outlined here is a schedule of minimum laboratory work to be obtained. These studies may be obtained more often by the patient's primary clinical team. Any lab test obtained by the primary team within 3 days for weekly labs or within one week for less frequent labs will be used in place of the research lab test.
 - iii. Of note all lab tests listed could be considered standard of care, with the exception of INR.
 - iv. Essential fatty acid profiles will be obtained every 4 weeks (28 days) while receiving study lipid regimen.
 - 1. Blood volume needed 0.3-1mL
 - 2. Considered standard of care in any patient on alternative lipid dosing, such as patients enrolled in this study.
 - 3. If diagnosed with essential fatty acid disorder, defined as triene:tetraene ratio >0.05:
 - a. If Smoflipid dose is less than 3 g/kg/d, SMOF will be increased by 0.5 g/kg/d or to 3 g/kg/d maximum
 - b. Those receiving Smoflipid at 3 g/kg/d will be changed to Intralipid at current Smoflipid dose
 - c. Those receiving Intralipid will have their dose increased by 0.5 g/kg/d to maximum of 3 g/kg/d
 - v. Total and fractionated bilirubin levels will be monitored at least once weekly (7 days)
 - vi. Liver function panel and gamma-glutamyl transferase (GGT) will be monitored at least every 2 weeks (14 days).
 - vii. Triglyceride levels will be monitored within the first 48 hours of lipid initiation and then once weekly (7 days).

1. If triglyceride level >250 mg/dL will decrease dose of study lipid by 1g/kg/d to minimum of 2 g/kg/d of Smoflipid or 1 g/kg/d three days per week for Intralipid

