2. Lipid infusion will be held if triglyceride level > 400 mg/dL
 - a. Once triglyceride level <400 mg/dL lipid infusion can be restarted. A lower dose can be used if deemed necessary by the primary care team and dietitian.

viii. Bleeding studies

1. Platelets will be monitored once weekly until stable (minimum 2 consistent values, 5-7 days apart) and then once every 4 weeks.
2. INR will be measured once weekly until stable (at least 2 consistent values, 5-7 days apart) and then once every 4 weeks.
 - a. Blood volume 1.7 mL
 - b. Because this lab is not standard of care, the cost will be covered by research funds, not by the individual patient.

ix. Glucose will be monitored at initiation of parenteral nutrition until stable and then with significant changes in glucose infusion rate. This can be performed via basic metabolic profile (BMP), point of care (POC) glucose, or any other lab source that provides a blood glucose measurement.

1. If the blood glucose is >200 mg/dL on more than one measurement separated by at least 3 hours, the primary team will consider decreasing the patient's GIR.
2. If blood glucose is <50 mg/dL the primary team will consider increasing the GIR.

x. Blood volume:

1. Minimum blood volume per each phlebotomy event are listed in Table 2.
2. Total minimum blood volume 24.4 mL per patient over the 14 blood draws during the study.

xi. Post-study monitoring:

1. As indicated in Table 2, triglyceride, hepatic function panel, GGT, essential fatty acid panel, platelet count, and INR will be measured 2-3 weeks post-study completion or at time of discharge, whichever comes first.
 - a. This time frame will be for all patients enrolled in the study, regardless of their length of time within the study.
 - b. If the patient is to be discharged from the hospital prior to this 2-3 week time period, labs will be drawn within 3 days of discharge, prior to leaving the hospital.

Table 2: Minimum laboratory requirements while enrolled in study (TG= triglyceride, HFP = Hepatic Function Panel, FB = fractionated bilirubin, GGT= gamma glutamyl transferase, EFA = essential fatty acids, PLT= platelet count) (Blood volume is minimum required to perform all tests listed)

	Week													
	0	1	2	3	4	5	6	7	8	9	10	11	12	+2-3
Test	TG	TG	TG	TG	TG	TG	TG	TG	TG	TG	TG	TG	TG	TG
	HFP	FB	HFP	FB	HFP	FB	HFP	FB	HFP	FB	HFP	FB	HFP	HFP
	GGT		GGT		GGT		GGT		GGT		GGT		GGT	GGT
					EFA				EFA				EFA	EFA
	PLT	PLT			PLT			PLT					PLT	PLT
	INR	INR		INR			INR				INR		INR	INR

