- iv. Subjects leaving the study secondary to parental request may not have further follow-up performed if at the request of the parent.

Historic Controls

Historic controls will have their charts reviewed to document the same information as for prospective patients. For historic controls, this information will be limited to their time admitted to Riley Hospital only. Information recorded will include:

- 1. Diagnosis and procedures:
 - a. Documentation of diagnosis making eligible for study participation
 - b. Documentation of surgery performed
- 2. Parenteral nutrition:
 - a. Length of parenteral nutrition: Documentation of total days of parenteral nutrition including start date, stop date, and dates not receiving parenteral nutrition.
 - b. Lipid dosing: maximum lipid dose, average lipid dose on weekly basis
 - c. Glucose dosing: documentation of glucose infusion rate (GIR) including maximum dose and weekly average GIR dose
 - d. Protein dosing: documentation of maximum amino acid dose received and weekly average amino acid dose
 - e. Discontinuation of parenteral nutrition: including reason for discontinuing and for what length of time.
- 3. Enteral Feeding:
 - a. Autonomy: the time from start of enteral feeding until complete enteral autonomy (enteral feeding only) will be documented for each patient.
 - b. Weekly enteral feeding: On a weekly basis an average of enteral feeding intake will be determined both in volume and calories. Based on these calculations a percentage of overall intake related to parenteral nutrition will be determined.

- c. Milk intake: The particular milk prescribed to each patient will be documented along with the particular form of additives and fortification used.
- 4. Measurements:
 - a. Weight, length, and head circumference will be recorded on a weekly basis for each patient.
 - b. Corrected measurements will also be obtained for each patient at 36 weeks corrected gestational age and the time of discharge from the Riley NICU. Given these are historic patients, the values obtain closest to these dates will be used for the purposes of this study.
- 5. Laboratory values:
 - a. Laboratory values listed above for prospective patients will be documented for historic patients if available within the electronic medical record.
 - b. If cholestasis is diagnosed the interventions and treatments received by the patients will be documented.
- 6. Diagnoses of prematurity

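### Read literally, the primary endpoint's 5-7 day window ends at the 7-day sampling interval, so raised bilirubin pairs 8 or more days apart go uncounted, and no counting period is stated

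*Combined protocol and SAP*

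**What the plan says.** All references are to the combined protocol and SAP.

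- **Endpoint** (Study Objectives, 1. Primary): "Cholestasis will be defined as direct bilirubin greater than 2 mg/dL for at least two measurements, 5-7 days apart".
- **Sampling** (Study Procedures, 3.e Laboratory monitoring, v): "Total and fractionated bilirubin levels will be monitored at least once weekly (7 days". Item ii calls the schedule a minimum and allows substitution: "Any lab test obtained by the primary team within 3 days for weekly labs" takes the place of the research lab. It does not say whether the substitute may be earlier, later or both. Item i adds: "Effort will be made to draw all study lab tests along with other standard of care, routinely scheduled labs".
- **Same phrase elsewhere** (3.e, viii Bleeding studies): "Platelets will be monitored once weekly until stable (minimum 2 consistent values, 5-7 days apart". INR has parallel wording.
- **Controls** (Historic Controls, 5. Laboratory values): "Laboratory values listed above for prospective patients will be documented for historic patients if available within the electronic medical record". No sampling interval is given for them.
- **Entry**: prospective infants are excluded at enrollment for "Direct bilirubin greater than 2 mg/dL on any consecutive measurement 5-7 days apart within 2 weeks of enrollment". Controls are ineligible if any "exclusion criteria are true at the time of their abdominal surgery".
- **Analysis** (Statistical Considerations): Fisher's exact test for categorical outcomes, with no rule on which bilirubin values count or over what period.

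**The concern.** A window of 5 to 7 days leaves no slack above a 7-day schedule. If one draw moves a day relative to the next, two raised values can fall 8 days apart and drop out, while a pair 5 days apart counts. The rule then discards the pair that shows the longer elevation.

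Three things are at stake.

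- The primary count would depend partly on when blood was drawn. Timing is guided by protocol in the two prospective arms and was set by past clinical practice in the controls.
- Two analysts could count differently, one holding to the closed window and the other accepting confirmation at the next weekly draw.
- No start or end of counting is given. Neither enrollment nor surgery is named as day zero for the endpoint. The exclusion requires a raised pair, so an infant with one raised value can enter, and the text does not say whether that value may be the first of a qualifying pair.

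**Working it through.** The plan states no event rate, power or expected number of cases, so it has no figure to reproduce. The check is of the gaps that the schedule allows.

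**Inputs.** Threshold and window: Study Objectives, 1. Interval of 7 days: 3.e(v). Tolerance of 3 days: 3.e(ii). Group sizes: 25 per arm (minimum 12) and 24 controls. The documents do not give the frequency of substitution. It is **assumed** here to be p = 25, 50 or 100% of draws, independent between draws, with whole-day shifts equally likely and one value per week.

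**1. Possible gaps.** Draw *i* falls on day 7*i* + s*i*, so an adjacent gap is 7 + s2 − s1.
- Substitutes only early (s from −3 to 0): from 7 − 3 = 4 to 7 + 3 = 10 days.
- Early or late (s from −3 to +3): from 7 − 6 = 1 to 7 + 6 = 13 days.
- Each draw timed from the last actual draw, early only: gap = 7 + s, from 4 to 7 days.

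**2. No loss.** If draws are exactly weekly, or keep a constant offset (s1 = s2), the gap is 7 and every pair qualifies.

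**3. Two raised values, p = 25%, literal window.**
- Early only: P(s = 0) = 0.75 + 0.25/4 = 0.8125, and each other shift has 0.0625. P(s1 = s2) = 0.8125² + 3 × 0.0625² = 0.6719. By symmetry P(gap ≥ 8) = (1 − 0.6719)/2 = 16.4%. P(gap ≤ 4) = 0.8125 × 0.0625 = 5.1%. Missed: 21.5%.
- Early or late: P(s = 0) = 0.75 + 0.25/7 = 0.7857, and each other shift has 0.0357. P(s1 = s2) = 0.7857² + 6 × 0.0357² = 0.6250. P(gap ≥ 8) = 18.8%. P(gap ≤ 4) = 2 × 0.7857 × 0.0357 + 8 × 0.0357² = 6.6%. Missed: 25.4%.
- Timed from the last draw: P(gap = 4) = 0.25/4 = 6.3%, and no gap exceeds 7.

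**4. Range, by exact enumeration.** An infant is missed when no pair among the raised values is 5-7 days apart.

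| Scenario | Raised weekly values | p = 25% | p = 50% | p = 100% |
|---|---|---|---|---|
| Early or late | 2 | 25.4% | 44.4% | 63.3% |
| | 3 | 9.6% | 21.8% | 39.7% |
| Early only | 2 | 21.5% | 35.9% | 43.8% |
| | 3 | 6.7% | 12.9% | 15.6% |
| Timed from last | 2 | 6.3% | 12.5% | 25.0% |
| | 3 | 0.4% | 1.6% | 6.3% |

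**5. With a 5-14 day window.** For p = 25%, the two-value miss falls to 6.6% (early or late) and 5.1% (early only). It stays at 6.3% if draws are timed from the last, because all of those misses are gaps under 5 days. With three or more raised values the miss is 0% in every scenario.

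**6. One infant.** One reclassification moves a group's rate by 1/25 = 4.0, 1/24 = 4.2 or 1/12 = 8.3 percentage points.

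**7. End of counting.** 3.e(xi) schedules a hepatic panel 2-3 weeks after study completion, or at discharge if sooner, when lipid is at the physician's discretion. At 14 days that sample could pair with a value on the day lipid stopped under a 5-14 day rule. A wider window therefore needs a stated end.

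**The case against.** The strongest reply is that the loss may be small or nil. Weekly sampling is a minimum. If 7 days is read as a ceiling, a gap of 8 or more days is already a departure from the schedule. Research draws are to be aligned with routine labs, which favours regular spacing. The endpoint counts measurements, not scheduled draws, so any extra clinical bilirubin can complete a pair. The 5-7 day phrase is also used for successive weekly platelet and INR values, so it may simply mean confirmed at the next weekly draw. All of this stands as a limit on size. It does not settle the wording: the endpoint has a closed window, and the substitution allowance can carry adjacent values beyond it.

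It can also be said that the start of counting is implied, since the objective speaks of infants on study lipid who develop cholestasis. That narrows the gap but leaves open a single raised value at or before enrollment.

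A reader might infer three stronger things that the documents do not support.

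- *A large share of cases will be lost.* The upper figures in the table need every draw to be substituted independently, and nothing in the plan suggests that.
- *The comparison with controls is biased.* Chart-only values may ascertain cases differently, but the controls' sampling frequency is not given, the direction is unknown, and bias is not shown.
- *The 3 mg/dL stopping criterion changes the endpoint.* Its interval is worded one way under Stopping study Lipid and Study Duration (with a minimum) and another under Individual Patient Stopping Criteria (as a closed range). It is a separate rule with a separate threshold and leaves the endpoint as it is.

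**Conclusion.** The point holds as a defect of definition. As written, the primary rule can leave out an infant whose raised values are 8 or more days apart, and it does not say when counting begins or ends. These two facts come from the text and need no modelling.

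The size is uncertain and starts at zero. Under the assumption of 25% independent substitution and one value per week, the literal rule misses 21-25% of infants with exactly two raised weekly values and 7-10% of those with three, or 6% and 0.4% if each draw is timed from the last. Of the two-value misses, 5 to 7 points (all 6 if timed from the last draw) are gaps under 5 days and are not caused by the upper limit. Longer runs of raised values and extra clinical draws shrink the loss further. With 12 to 25 infants in a group, even one reclassified infant is visible in the rate, so the wording should be settled before cases are counted.

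**What to change.** For the analysis, define the primary endpoint as direct bilirubin above 2 mg/dL on two measurements at least 5 and at most 14 days apart, both within a stated counting period:

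- prospective infants: from study-lipid start to study-lipid stop;
- controls: from a stated time zero to lipid stop, with the same 84-day cap.

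The post-study sample then cannot define a case. The 14-day limit covers the largest adjacent gap (13 days). Apply the rule identically to all three groups. Do not add a condition on intervening values to the primary rule: that would be a new restriction, and it would fall hardest on infants sampled most often.

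Report the number and spacing of bilirubin values by group, and give the literal 5-7 day window as a sensitivity analysis. Two further analyses are optional: one requiring no intervening value of 2 mg/dL or below, and one leaving out infants above 2 mg/dL at time zero.

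The cost is a change of wording, one table and one sensitivity analysis, with no extra blood draws. Case counts may rise slightly, and a longer gap may hide a normal value in sparsely sampled infants; the spacing table and the sensitivity analysis help show whether this matters. Gaps under 5 days in infants with only two raised values stay uncounted.

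Separately, the sponsor must reconcile the interval wording of the 3 mg/dL stopping criterion across the three sections named above. No stopping or eligibility rule is proposed here.
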